## **Scientific background**

Accumulating evidence suggests an imbalance between habitual and goal-directed behavior in favor of habitual control in parallel with an exaggerated tendency toward compulsive/harm avoidance behavior in OCD. However, the underlying neural mechanism of habitual/goal-directed imbalance in OCD has yet to be investigated.

## **Objective**

The objective of this project was to explore the neurobehavioral characteristics of an arbitration mechanism, which has been demonstrated to regulate contributions of goal-directed and habitual strategies of action selection in non-clinical populations, in OCD.

## **Design**

We recruited 30 male and female adults (age 18-65) with OCD and 30 age-, sex-, and education-matched healthy (medically, neurologically and psychiatrically) controls for this project. Each participant came for three sessions. There were 3-8 days interval between sessions:

Session 1 that included initial clinical assessment and obtaining T1 structural image.

Session 2 and 3 that included performing two separate decision-making and symptom provocation-avoidance tasks (see below for more information) by participants with OCD and healthy controls under two conditions: while scanned inside the MRI scanner (no tDCS) or while receiving tDCS neurostimulation outside the scanner (no fMRI imaging). As participants performed each task twice, there might be an order effect on task performance. For minimizing the impact of such a potential order effect on imaging and tDCS results, participants were randomly assigned to undergo scanning in the session 2 and then receive tDCS in the session 3

or in the opposite order (tDCS in session 2 and then imaging in session 3) but in each session only one of imaging or tDCS experiments (for both tasks) could be conducted for each participant.

OCD-relevant and aversive picture rating (explained below) could be done always in the session 3 as the last experiment.

### **Methods:**

We examined the activity and connectivity patterns of the arbitration regions that have been previously determined to comprise the right and left inferior lateral prefrontal cortex (ilPFC) and right frontopolar cortex (FPC) in individuals with OCD. We acquired functional magnetic resonance imaging (fMRI) data while participants performed a decision-making (DM) task in which goal-directed and habitual action selection strategies compete to govern behavior control. Furthermore, we tested activity and network connectivity of the arbitration regions during the performance of a more clinically relevant symptom provocation-avoidance (SP-A) task. To additionally probe this mechanism, we used the non-invasive brain stimulation method of transcranial Direct Current Stimulation (tDCS). Excitatory and inhibitory currents applied by tDCS over a targeted arbitration region, the left ilPFC, while participants performed the DM and SP-A tasks to further corroborate whether the target arbitrator has causal effects on task performance and habitual/goal-directed action selection balance.

### **Statistical analysis plan:**

For this study we assumed a data loss of about 10% leading to a final usable data sample size of  $n=30$  OCD participants and 30 age-, sex, and education matched healthy controls for a final sample size of  $n=60$ . This sample size could provide sufficient power ( $>.8$ ) to detect group differences of  $d=.73$ , and associations between continuous variables as small as  $r=.35$ . For regression analyses within the OCD sample, we are able to detect associations as small as  $r=.48$  reliably (power $>.8$ ). In Gillan et al, 2015 study (fMRI imaging of avoidance decision-making in OCD), the differences in the BOLD signal in the medial orbitofrontal cortex during acquisition of avoidance between OCD and controls showed effect sizes of  $d=1.23$ , and during overtraining of avoidance effect sizes of 1.19. Association between behavioral measures (urge to respond) and activity in the caudate showed an effect size of  $r=.63$ . The proposed study provides a power of  $>.99$  for effects of this size, and based on this we consider this study to be sufficiently powered for the fMRI aims. Effect sizes in Gillan et al., 2011 study, for the association between a behavioral measure comparable to the paradigm proposed here and OCD symptom severity is  $r=.56$ , an effect size that can be reliably (power=.91) detected in the OCD sample in this study ( $n=30$ ). In a comparable tDCS/decision making study (Weissengruber et al. 2020), showed the behavioral effects of cathodal stimulation with effect sizes of  $d=.77$  for model-free action selection, and  $d=.65$  for reduction of switching. The proposed sample size provides power of .97 and .92 respectively to detect effects of this size. Based on these studies with comparable experimental design, we consider the proposed project to be sufficiently powered to detect the OCD related group differences in both behavioral and imaging data, association between behavioral and imaging data, and effects of tDCS on behavioral performance in an instrumental decision-making experimental paradigm.

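### The SAP counts 30+30 as usable after about 10% loss, the Design section reports 30+30 recruited, and the available text does not reconcile the two

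*Combined protocol and SAP*

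**What the plan says.** The Statistical analysis plan section starts from an allowance for loss: "For this study we assumed a data loss of about 10% leading to a final usable data sample size of" 30 "OCD participants and 30 age-, sex, and education matched healthy controls for a final sample size of" 60. On that basis it continues "This sample size could provide sufficient power", meaning above .8, for a group difference of d=.73 and for a correlation of r=.35. It claims the same power for r=.48 within the OCD group. For a published correlation of r=.56 it calls this "an effect size that can be reliably (power=.91) detected in the OCD sample in this study", with n=30.

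The Design section, in the past tense, says "We recruited 30 male and female adults (age 18-65) with OCD and 30 age-, sex-, and education-matched healthy" controls, and then "Each participant came for three sessions". It places imaging and stimulation in different sessions: "but in each session only one of imaging or tDCS experiments (for both tasks) could be conducted for each participant".

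No other available section gives an enrolment above 30 per group, a number lost, or a statement that the 30+30 are those with usable data. One part of the document was removed before review. Alpha and sidedness are not stated.

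**The concern.** Recruitment comes before loss. If 30 per group remain after a 10% allowance, more than 30 per group must have been enrolled. If 30 per group were enrolled and the allowance was used up, fewer than 30 remain. Both sections give the same number for what should be two different counts.

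This matters because the three claims of power above .8 are set close to their limit at 30+30, so a small loss takes them under it. Imaging and tDCS data also come from separate sessions, so the usable count may differ between the two sets of analyses, and a reader cannot tell which count applies to which.

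**Working it through.** **Inputs.** From the Design section: 30+30 recruited. From the Statistical analysis plan section: loss of about 10%; 30+30 usable; d=.73, r=.35 (N=60) and r=.48 (n=30) at power above .8; r=.56 (n=30) at .91; cited group effects d=1.23 and d=1.19. Assumed: two-sided alpha of .05, and equal loss in both groups that affects every analysis. The SAP's remaining power figures are not rechecked here.

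**Head count.** Enrolment needed for 30 usable: 30/0.9 = 33.3 per group (33 × 0.9 = 29.7; 34 × 0.9 = 30.6). Usable from 30 enrolled: 30 × 0.9 = 27.

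**Formulas** (n per group, N in the correlation):

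- d, normal approximation: Φ(d√(n/2) − 1.96)
- d, noncentral t: 2n − 2 df, noncentrality d√(n/2)
- r, Fisher z: Φ(atanh(r)√(N − 3) − 1.96)
- r, regression F: 1 and N − 2 df, noncentrality N r²/(1 − r²)

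**The plan's figures at 30+30.** For d=.73 the normal approximation gives .73 × √15 = 2.827, and Φ(2.827 − 1.96) = .807. For r=.56, Fisher z gives .6328 × √27 = 3.288, and Φ(3.288 − 1.96) = .908, the stated .91.

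**The same formulas after loss:**

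| Effect | Method | 30+30 | 28+28 | 27+27 |
|---|---|---|---|---|
| d=.73 | normal | .807 | .780 | .765 |
| d=.73 | noncentral t | .794 | .765 | .749 |
| r=.35, both groups | F | .812 | .784 | .769 |
| r=.35, both groups | Fisher z | .788 | .758 | .742 |
| r=.48, OCD only | F | .825 | .796 | .780 |
| r=.48, OCD only | Fisher z | .776 | .744 | .727 |
| r=.56, OCD only | Fisher z | .908 | .886 | .873 |

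- **Effect of loss.** From 30+30 to 27+27 the three claims lose 4.2 to 4.9 points within a given method. With two lost per group, all three are below .8 under both methods shown for each.
- **Effect of the formula.** At 30+30 only the normal approximation (d) and regression F (r) exceed .8. Noncentral t and Fisher z already give .776 to .794.
- **Method not identifiable.** F meets the r=.35 and r=.48 claims but gives .947 for r=.56. Fisher z gives .91 for r=.56 but misses the other two.
- **Sidedness.** One-sided .05 at 27+27 keeps all three above .8: .842 (d=.73, noncentral t), .833 (r=.35, Fisher z) and .820 (r=.48, Fisher z). It gives .950 for r=.56 at n=30, however, not the stated .91.
- **Large cited effects** (noncentral t, 30+30 to 27+27): d=1.23, .997 to .993; d=1.19, .995 to .990.
- **Detectable at 80% power, 27+27:** d = .763 (normal) to .777 (noncentral t); r = .362 (F) to .373 (Fisher z) in both groups; r = .489 (F) to .517 (Fisher z) in OCD only.

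**The case against.** The strongest reply is that nothing is miscalculated. The SAP section is a planning statement, consistent within itself, and the Design section is a report after the fact. The sentence that every participant attended three sessions suggests that the 30+30 are completers. If so, or if 30+30 were enrolled and none was lost, both sections can stand.

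Much of this holds. A reader might infer that the Design section misreports enrolment, but the documents do not show that: with no loss, 30+30 recruited is correct as written. A reader might also infer that the study was underpowered. That does not follow either, because it needs 30+30 to be the enrolled number, data to have been lost, and a two-sided test. Nor should the whole shortfall be put down to loss. For r=.48 by Fisher z, 2.4 of the 7.3 points below .8 are already present at 30+30. Finally, the SAP argues adequacy from published effects more than from its minimum detectable effects, and those recomputed here stay at .87 or above at 27+27.

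What remains is that attending three sessions is not the same as giving usable scan and task data, which is the count on which the SAP relies. The available text does not connect the two.

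**Conclusion.** The two sections use 30+30 for different things, and the available text does not reconcile them. This is an inconsistency in the reported basis of the power statement, and it does not show that the study failed to reach its planned size.

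The power consequence is conditional and modest. If 30+30 was enrolled and the plan's own 10% was lost, power for the three minimum detectable effects falls by about 4 to 5 points to between .727 and .780, and power for r=.56 falls from .91 to .87. This rests on two-sided .05, which the documents do not state but which fits the .91 better than one-sided .05 does, and on equal loss across groups and analyses. The conclusion that the study can detect group effects as large as those cited is hardly affected.

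**What to change.** State enrolled and usable numbers per group, separately for the fMRI and tDCS analyses, for example: *We enrolled [a] adults with OCD and [b] matched controls; [c] and [d] gave usable data for the fMRI analyses and [e] and [f] for the tDCS analyses.* Then, according to what happened:

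- More than 30 per group enrolled: give that number in the Design section.
- 30+30 enrolled and no data lost: say so, and leave the Design section as it is.
- 30+30 enrolled and data lost: restate the power figures at the actual usable count. At 27+27 the effects detectable at 80% power are about d=.76–.78, r=.36–.37 in both groups and r=.49–.52 in OCD only.

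In every case, state the alpha, the sidedness and the power method used.

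The cost is wording only, with no change to any endpoint or analysis. The one downside is that the stated detectable effects may become slightly less favourable.

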## **Behavioral data analysis for neurostimulation experiments:**

The effect of anodal (excitatory), cathodal (inhibitory) or sham tDCS stimulation on the prevalence of model-based (MB) and model-free (MF) action selection (number of trials in which MB or MF strategy could be used for action selection) and their ratio could be tested during the decision-making task performance. ANOVA and linear mixed-effects model could be applied, respectively, to compare the effect of different stimulation conditions (anodal, cathodal and sham) on behavioral performance and to compare the effect of two active stimulations (anodal, cathodal) as separate condition factors against sham, while controlling for the time factor between baseline (imaging with no tDCS) and tDCS sessions and treating participants as random effects. For symptom provocation-avoidance task, the effect of anodal, cathodal or sham tDCS stimulation could be evaluated on the timing of avoidance behavior (the duration of time that participants tolerate the OCD-relevant or aversive pictures before pushing the stop button).

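### The stated tDCS power (.97/.92) fits a paired test in about 28–30 people, but the design described most likely compares stimulation conditions between people, where those values need a high, unstated correlation

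*Combined protocol and SAP*

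**What the plan says.** The section headed Statistical analysis plan assumes 60 usable participants, 30 with OCD and 30 controls. It makes two statements that bear on this point.

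- For comparisons between groups: "This sample size could provide sufficient power ( $>.8$ ) to detect group differences of" d=.73.
- For tDCS, it cites "behavioral effects of cathodal stimulation with effect sizes of $d=.77$ for model-free action selection" and d=.65 for reduced switching, and then says: "The proposed sample size provides power of .97 and .92 respectively to detect effects of this size". It goes on to count "effects of tDCS on behavioral performance in an instrumental decision-making experimental paradigm" among the aims for which the study is sufficiently powered.

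The Design section says that each task was performed twice, once in the scanner without tDCS and once with tDCS outside it, and that "in each session only one of imaging or tDCS experiments (for both tasks) could be conducted for each participant".

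The section on behavioral analysis for the neurostimulation experiments plans an ANOVA across anodal, cathodal and sham. It also plans a mixed model to "compare the effect of two active stimulations (anodal, cathodal) as separate condition factors against sham". The repeated measure in that model is the no-tDCS scan, and the model is to be fitted "while controlling for the time factor between baseline (imaging with no tDCS) and tDCS sessions and treating participants as random effects".

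No section says how people are assigned to the three stimulation conditions, or how many are in each.

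**The concern.** The two power statements sit in one paragraph and refer to the same 60 people. A between-group difference of .73 is given power of about .8, yet a smaller effect of .65 is given .92. Both can be true only if the second rests on a different kind of comparison, such as a paired one, or on a gain from adjustment that the plan does not mention.

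The Methods section uses tDCS to test whether the left ilPFC has a causal effect on the balance between habitual and goal-directed action. If power is really .97/.92, a null result says a good deal against the cited effects. If it is nearer .66/.52, a null result says much less. The reader of the results needs to know which applies.

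**Working it through.** **Inputs.** From the Statistical analysis plan: d=.77 and .65, stated power .97 and .92, and N=60 (30+30). Alpha and sidedness are not stated. The plan's own power of .91 for r=.56 at n=30 recomputes by Fisher's z as Φ(0.633·√27 − 1.960) = .908 two-sided (one-sided .950), so two-sided .05 is assumed. All power values below use the noncentral t distribution. Pairs are for d=.77/.65.

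**1. Reproducing the stated figures.** Paired or one-sample test: ncp = d√n, df = n−1.

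| n | d=.77 | d=.65 |
|---|---|---|
| 28 | .975 | .912 |
| 29 | .979 | .922 |
| 30 | .983 | .931 |

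These match .97/.92 closely. A one-sided paired test at n=23 also fits (.973/.915), so the origin of the figures is not established. A paired test in all 60 gives 1.000/.999 and does not fit.

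**2. Between-person comparison, unadjusted.** ncp = d√(n₁n₂/(n₁+n₂)), df = n₁+n₂−2.

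- Plan's benchmark, 30 v 30, d=.73: ncp = .73√15 = 2.83, power .794. This agrees with the stated value of about .8.
- 30 v 30, the best two-condition split of 60: ncp = 2.98/2.52, power .835/.697 two-sided and .904/.800 one-sided.
- 20 v 20, an equal three-way split: ncp = .77√10 = 2.43 and .65√10 = 2.06, power .660/.517.
- Reaching .97 and .92 two-sided needs 51 and 55 per condition, that is 102 and 110 people.

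**3. Which comparison the design allows.** Each task is done twice: one performance is the no-tDCS scan and the other is the tDCS session. The repeated measure named for the mixed model is the no-tDCS scan. That leaves no second stimulation session for a within-person contrast of cathodal with sham. A paired comparison of no-tDCS with cathodal in 20 people gives .904/.787, and it confounds stimulation with being in or out of the scanner.

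**4. Allowing for the no-tDCS session.** Assume 20 per condition pooled over diagnosis, a between-group d, no multiplicity correction, and correlation r between the two sessions.

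- Covariate: effect d/√(1−r²), df = 2n−3.
- Condition-by-time (change score): effect d/√(2(1−r)), df = 2n−2.

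| r | covariate | change score |
|---|---|---|
| .3 | .701/.555 | .518/.395 |
| .5 | .782/.637 | .660/.517 |
| .7 | .913/.800 | .865/.734 |
| .8 | .977/.916 | .963/.886 |

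Solving for the stated power gives r=.787 (for .97) and .804 (for .92) with the covariate, and r=.809 and .823 with the change score. At r=.5 the change-score effect is d/√1 = d, the same as unadjusted. Below .5 it is smaller.

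**5. If the cited d is within-person.** Let c be the correlation in the cited study and r the one here. The between-group d is then d√(2(1−c)). The covariate effect is d√(2(1−c)/(1−r²)), and the change-score effect is d√((1−c)/(1−r)).

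- For non-negative r no higher than c, these are at most d√2 and d. Power is then at most .918/.808 (covariate) and .660/.517 (change score).
- If r is sufficiently higher than c, the stated values can be passed: c=0 and r=.6 give .987/.943 with the covariate.

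**The case against.** The strongest reply is that the allocation is inferred. The plan limits each session to imaging or tDCS, but it does not say that a person receives only one stimulation condition within the tDCS session. The stated figures fit a paired test at about 30, the size of each diagnostic group, so a within-person plan is a live reading. This stands. A reader might infer that the plan's power is simply wrong, or that the figures are known to come from a paired test in one diagnostic group. The documents support neither. The first depends on the between-person reading, and the second is only one of the calculations that fit.

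A second reply is that the planned contrast of active stimulation with sham is a mixed model that uses the no-tDCS session, so an unadjusted limit is not the right yardstick. This also stands in part: adjustment can reach the stated power. But it needs a correlation of about .8 under the assumptions used here, and the plan gives neither the correlation nor the form of the model.

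A third reply is that the type of the cited d cannot be settled from these documents. That is so, and it leaves open a case in which the stated power is exceeded. That case needs a correlation here sufficiently higher than in the cited study, which the plan does not argue.

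A reader might also infer that the test is more likely than not to miss the effects. Most of the figures do not show that. Unadjusted, the miss rates are 34% and 48%; with the covariate at correlation .5 they are 22% and 36%. Among the adjusted cases tabulated, only d=.65 with a change score at correlation .3 (power .40) falls below one half.

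**Conclusion.** Two things are certain. The basis of .97/.92 is not stated, and those values cannot come from an unadjusted between-person comparison of these 60 people, whether one-sided or two-sided.

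The rest is conditional. The Design and behavioral analysis sections make a between-person comparison of anodal, cathodal and sham the most likely reading. On that reading the power sentence is not supported as written, unless the correlation between sessions is high or, for a within-person d, sufficiently above that in the cited study. The size of the gap rests on the assumptions stated in the working: equal thirds, pooling over diagnosis, two-sided .05, no multiplicity correction and a between-group d.

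Unless such a correlation can be justified, the tDCS test is materially more likely to miss the cited effects than the implied 3% and 8%. A null result should not then be taken as strong evidence against a causal role for the left ilPFC.

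**What to change.** Replace the .97/.92 sentence with power for the contrast and model actually planned. State the allocation to conditions, the number in each, alpha and any multiplicity correction, the type of d and the assumed correlation. If inputs are unknown, give a range, for example:

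*Assuming 20 per condition pooled over diagnosis, two-sided alpha .05, no multiplicity correction, a between-group d and the no-tDCS session as a covariate, power for cathodal v sham at d=.77/.65 is .70/.56, .78/.64 and .91/.80 at correlation .3, .5 and .7 (.66/.52 unadjusted).*

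If the mixed model tests condition-by-time as a change score, use .52/.40, .66/.52 and .87/.73 instead.

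In the behavioral analysis section, specify that the no-tDCS session enters as a covariate, or that condition means are constrained equal at that session. This may only clarify what is already intended. It matters because the change-score form has less power than no adjustment when the correlation is below .5.

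If conditions were compared within the single tDCS session, say so and justify the paired figure.

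Remove "effects of tDCS on behavioral performance in an instrumental decision-making experimental paradigm" from the aims called sufficiently powered unless the restated figure supports it.

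The cost is wording only. The stated power becomes less favourable, and no extra participants are needed.

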## ***Imaging (fMRI) data analysis:***

In the 1st level (within subject) analysis, we could contrast BOLD signal during decision-making, OCD- and aversive- relevant stimuli presentation compared to a (cross-hair) baseline. The General Linear Model (GLM) method with permutation testing for group-level comparisons could be applied to measure the level of activity ***in the regions of interest*** derived from Lee et al. study for the arbitration (the right and left ilPFC and right PFC), habitual (posterior putamen and supplementary motor area) and goal-directed regions (the vmPFC and caudate) during the decision-making task. For the symptom provocation-avoidance task, the total duration of photo presentation, defined as *avoidance timing*, could be divided into two intervals: 1) starting time of photo presentation until 1-second before pushing the stop button (exposure period), and 2) the 1-second period just before pushing the button. The second interval that

models the avoidance decision period in an approach similar to the Banca et al. study could be focused to test our hypotheses. For all regions mentioned above, activity level could be measured during the avoidance decision period (1 s) by employing GLM with permutation testing for group-level comparisons.

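### Does the behaviour-imaging association need a stated sample and a diagnosis term before the power claim for it can stand?

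*Combined protocol and SAP*

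**What the plan says.** The Statistical analysis plan section ends by declaring the study "sufficiently powered to detect the OCD related group differences in both behavioral and imaging data, association between behavioral and imaging data", together with effects of tDCS on behaviour.

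Earlier in that section there are two general benchmarks. One follows the total of 60 and covers group differences of d=.73 "and associations between continuous variables as small as" r=.35. The other is for patients only: "For regression analyses within the OCD sample, we are able to detect associations as small as" r=.48. Neither is assigned to the behaviour-imaging association.

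One cited result is of that type: urge to respond against caudate activity, r=.63, for which power above .99 is claimed with no sample size in the sentence. The only association tied to a sample is behaviour against symptom severity: r=.56, power .91, in the 30 patients.

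The section on neurostimulation experiments uses ANOVA and a mixed model to "compare the effect of different stimulation conditions (anodal, cathodal and sham) on behavioral performance". The Imaging (fMRI) data analysis section measures regional activity by "employing GLM with permutation testing for group-level comparisons". Neither relates a behavioural measure to BOLD signal, and neither mentions diagnosis as a covariate.

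**The concern.** Of the three things the study is said to be powered for, two have an analysis described and one has none. Its sample is open as well.

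If both groups were used, the handling of diagnosis would decide what is estimated. The same closing sentence looks for patient-control differences in behaviour and in imaging. If both exist, a correlation over all 60 people that ignores diagnosis mixes two statements: patients differ from controls on both measures, and activity tracks behaviour among people of the same diagnosis. Matching on age, sex and education does not separate them, because the differences of interest come with diagnosis itself.

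A pooled correlation could therefore appear with no relation inside either group, or be masked if the two differences run in opposite directions. With sample and model both unwritten, the choice could also be made after the results are seen.

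**Working it through.** **Inputs.** From the Statistical analysis plan section: 30 patients and 30 controls; r=.35, .48, .56 and .63; detectable d=.73; cited BOLD group differences d=1.23 and 1.19. Assumed, because the documents do not state it: two-sided alpha .05. The documents give no patient-control d for behaviour, so every behavioural d below is an assumption.

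**Step 1: the plan's own figures.** Fisher z power is Φ(atanh(r)·√(n−3−k) − 1.96), where k is the number of covariates.

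| r | n | Calculation (k=0) | Power | Plan says |
|---|---|---|---|---|
| .56 | 30 | .633 × 5.196 − 1.96 = 1.33 | .908 | .91 |
| .63 | 30 | .741 × 5.196 − 1.96 = 1.89 | .971 | >.99, no n given |
| .63 | 60 | .741 × 7.550 − 1.96 = 3.64 | .9999 | >.99, no n given |
| .35 | 60 | .365 × 7.550 − 1.96 = 0.80 | .788 | >.8 |
| .48 | 30 | .523 × 5.196 − 1.96 = 0.76 | .776 | >.8 |

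The last two reach .812 and .825 with a noncentral F test, so the stated figures hold within the choice of method.

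**Step 2: which sample does >.99 imply?** By the method that reproduces .91, r=.63 passes .99 only at n=60. That suggests both groups but does not settle it: the noncentral F test gives .990 at n=30, although it gives .947 rather than .91 for r=.56.

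**Step 3: what pooling without diagnosis would do.** With within-group correlation ρ and group differences d₁ and d₂, the pooled correlation in equal groups is (ρ + d₁d₂/4) / √[(1 + d₁²/4)(1 + d₂²/4)].

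- ρ=0, d=.5 on both: .0625/1.0625 = .059.
- ρ=0, d=.73 on both: .1332/1.1332 = .118.
- ρ=.35, d=.5 on both: .388 if the differences run with the slope, .271 if against it.
- ρ=.35, d=.73 on both: .426 or .191.

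Simulated rejection rates with ρ=0 and 30+30 (100,000 data sets per row):

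| d imaging | d behaviour | Diagnosis omitted | Diagnosis included |
|---|---|---|---|
| .73 | 0 | 5% | 5% |
| .3 | .3 | 5% | 5% |
| .5 | .5 | 7% | 5% |
| .73 | .73 | 15% | 5% |
| 1.23 | .5 | 16% | 5% |
| 1.23 | .73 | 28% | 5% |

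**Step 4: cost of including diagnosis.** With k=1 at n=60, power at r=.35 is Φ(.365 × 7.483 − 1.96) = Φ(0.775) = .781, against .788 without it. At r=.63 it is .9998.

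**Step 5: does one adjusted slope answer the question?** Only if the relation is the same in both groups. With r=.6 in one group and 0 in the other, the diagnosis-adjusted correlation averages about .30 and describes neither; with +.5 and −.5 it averages zero.

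**The case for a change.** The strongest case for a change is that an explicit power claim deserves an analysis, that the >.99 figure makes pooling a real possibility, and that one or two sentences would close the gap at a cost of one degree of freedom. The cited imaging differences of 1.23 and 1.19 also mean that .73 is no ceiling, so the distortion could be larger than the plan's detectable difference suggests.

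Most of that stands as description: the text is silent, pooling is plausible, and the arithmetic is sound. It does not show the plan to be wrong. No section says that groups will be pooled without diagnosis, and the distortion needs pooling, omission of diagnosis and a group difference on both measures together. If only one measure differs, or if the analysis is confined to patients, there is none.

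A prescribed covariate sentence would also go further than the documents support. The Objective section describes exploratory work, in which a whole-sample association is a different target and not automatically a mistake. Making a common within-group slope the claim would bring in an equal-slopes assumption that a study of altered arbitration in OCD has no clear reason to make.

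**Conclusion.** The observation is accurate, but it is a gap in detail. The plan's power figures reproduce under two-sided .05, allowing for the choice of method, and no two statements conflict. An analyst working with two diagnostic groups would ordinarily either analyse the patients alone or account for group and look at the slopes separately. Both routes are open under the plan as written, and the group term costs less than one percentage point of power at r=.35.

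The distortion, if the least careful option were taken, runs from nothing (a difference on one measure only) through 7% and 15% (d=.5 and .73 on both) to 28% (imaging d=1.23 with behavioural d=.73). All of these assume zero within-group correlation, 30 per group and behavioural differences that the documents do not supply.

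The point is best kept for reading the results. A reported behaviour-imaging association should come with its sample and its handling of diagnosis. If it is confined to patients, the relevant benchmark is r=.48, and power at r=.63 is about .97 by Fisher z. No change to the plan is needed.
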